6. TRIAL OUTCOME MEAURES AND PURPOSE

6.1. Primary Outcome Measure

The primary outcome measure for this study is to assess the safety and tolerability of ATI-502 Topical Solution, 0.46% in subjects with moderate to severe atopic dermatitis.

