9.3. Subject Withdrawal Criteria

Subjects will be informed that they are free to withdraw from the study at any time and for any reason. The investigator may remove a subject from the study if, in the investigator's opinion, it is not in the best interest of the subject to continue the study. Examples of other reasons subjects may be discontinued from the study are: a change in compliance with an inclusion or exclusion criteria, occurrence of AEs, occurrence of pregnancy, use of a prohibited therapy or subject is unwilling or refuses to continue with the protocol defined procedures, treatments and/or study visits and/or subject withdraws consent.

The date the subject is withdrawn from the study and the reason for discontinuation must be recorded in the subject's electronic case report forms (eCRFs). All withdrawn subjects will be required to complete one last safety follow up visit approximately 30 days after last study medication application. If the subject withdraws their consent to have this visit completed this needs to be appropriately documented in the subject's source notes and on the subject's eCRF.

Subjects will be permanently discontinued from the study in the event of any of the following:

- Severe infection requiring parenteral antimicrobial therapy or hospitalization
- Symptomatic herpes zoster

- Malignancy – except for non-melanoma skin cancer (SCC or BCC) not in or near the treatment area
- Anaphylactic or severe allergic reaction
- WBC Count: $< 1 \times 10^9/L$ or second occurrence of $< 2 \times 10^9/L$
- ANC: $< 0.5 \times 10^9/L$ or second occurrence of $< 1 \times 10^9/L$
- Lymphocyte count: $< 0.3 \times 10^9/L$ or second occurrence of $< 0.5 \times 10^9/L$
- Platelet count: $< 50 \times 10^9/L$ or second event of $< 75 \times 10^9/L$ - in each case, value should be confirmed by retesting before treatment discontinuation
- Hemoglobin: $< 6.5 \text{ g/dL}$ or second occurrence of $< 8 \text{ g/dL}$ - in each case, value should be confirmed by retesting before treatment discontinuation
- AST or ALT:
 - $> 5 \times \text{ULN}$ persisting for 2-weeks of study medication interruption or second event of $> 5 \times \text{ULN}$
 - $3 \times \text{ULN}$ with total bilirubin $> 2 \times \text{ULN}$ or symptoms of hepatocellular injury [fatigue, nausea, vomiting, right upper quadrant pain or tenderness, fever, rash and/ or eosinophilia ($> 5\%$)].

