13.2. Adverse and Serious Adverse Events

13.2.1. Definition of Adverse Events

13.2.1.1. Adverse Event (AE)

An AE is the development of an undesirable medical condition or the deterioration of a pre-existing medical condition following or during exposure to a pharmaceutical product, whether or not considered casually related to the product. In clinical studies, an AE can include an undesirable medical condition occurring at any time, including baseline or washout periods, even if no study treatment has been administered.

The investigator should, when certain, report a diagnosis rather than the signs, symptoms or clinically significant abnormal laboratory values associated with the AE. Otherwise, signs, symptoms or abnormal laboratory values may be used to describe the AE.

Any CS abnormality discovered prior to the first study medication treatment should be reported as medical history, not as an AE.

All AEs that occur from the time of first study medication application (Visit 2) until 30 days after last study medication application must be documented in the subject's source documents and in Aclaris' EDC system.

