## 2. STUDY DESIGN

This is an open label, multicenter, phase 2a study designed to evaluate the safety and tolerability of ATI-502 Topical Solution, 0.46% in male and female subjects with a diagnosis of AD as defined by the Hanifin and Rajka criteria. Based on the 5-point Physician's Global Assessment (PGA) scale, subjects must have a score of 3 (moderate) or 4 (severe). Subjects will be required to apply ATI-502 study medication to their identified AD treatment areas twice a day (BID) for a total of 4 weeks. Subjects will be allowed to treat new disease areas with ATI-502 Topical Solution, 0.46% if they appear after Visit 2. All subjects will be required to complete a safety follow up visit 4 weeks post last study medication application.

A total of 30 evaluable subjects who are  $\geq$  18 years of age with a clinical diagnosis of moderate or severe AD will be enrolled to the study.

Safety and tolerability will be evaluated by assessment of adverse events, physical examinations, vital signs, ECGs and clinical laboratory tests.

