#### **4.2.2 Signs of Atopic Dermatitis (SAD)**

For each symptom (erythema, induration, lichenification, excoriation, exudation), the number and percentage of subjects with a score of 0 (none),  $\leq 1$  (None or Mild) and improved by at least 1 level from baseline will be tabulated by visit. This categorical summary for the SAD will be conducted on both the Efficacy Population and the PP population, separately.

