#### **4.3.1 Adverse Events**

Adverse events will be coded using the MedDRA dictionary V21.1 and will be categorized by system organ class (SOC) and preferred term (PT). Only treatment emergent adverse events will be included in summary tabulation. All adverse events, including those that are not considered treatment emergent, will be included in the data listings.

To differentiate the study period in which an Adverse Event occurred, three categories will be defined based upon onset date. Adverse Events that had onset dates prior to the first application of study medication will be considered "prior". Adverse events with onset dates on or after the first application of study medication and within 30 days following the last application of study medication will be considered "on therapy" or equivalently "treatment emergent". Events with onset dates more than 30 days after the last application of study medication will be considered as "post-therapy".

Frequency tabulations will be presented by MedDRA SOC and preferred term, for all adverse events; study treatment-related, adverse events resulting in discontinuation of study treatment, serious adverse events and adverse events by maximum severity. Adverse events resulting in discontinuation will be those with 'action taken' recorded as 'drug withdrawn'.

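### The tolerability tables omit treatment holds and missed doses, and SAD and PGA are counted only in the favourable direction

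*SAP*

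**What the plan says.** **How tolerability is assessed.** Protocol 6.1 makes safety and tolerability the primary outcome, and Protocol 14.1 treats the related parameters as the primary analysis variables, summarised descriptively. SAP 2 names the tools: "Safety and tolerability will be evaluated by assessment of adverse events, physical examinations, vital signs, ECGs and clinical laboratory tests". No local tolerability scale is listed.

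**Adverse events.** SAP 4.3.1: "Frequency tabulations will be presented by MedDRA SOC and preferred term, for all adverse events", and also for related events, events leading to discontinuation, serious events and events by maximum severity. One of these five uses action taken: "Adverse events resulting in discontinuation will be those with" the action recorded as drug withdrawn.

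**Holds and missed doses.** Protocol 11.3 calls for a temporary hold after severe related adverse events or the laboratory values in its Table 4. Protocol 11.7 has sites document missed doses. SAP 4.1.7 summarises duration of treatment, total weight, total volume and average volume per application. SAP 4.1.2 gives study completion status and reasons for discontinuation. SAP 4.3.5 counts subjects meeting hepatobiliary and renal criteria, which it does not define.

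**Signs at target areas.** Under Protocol 12.4 the investigator grades five signs from 0 to 3 in each target area at Visits 2 to 6. SAP 4.2.2 tabulates a score of 0, a score of 1 or less, and "improved by at least 1 level from baseline will be tabulated by visit". SAP 4.2.3 tabulates PGA of 1 or less and PGA of 0.

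**The concern.** With no control arm and no inferential statistics, the descriptive tables are the whole of the primary result. For a topical product, two things a reader wants to know are how many subjects had to pause treatment and how many had worse skin where the product was applied. The planned tables answer neither directly.

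A subject whose dosing is held and never restarted, but who attends Visit 6, could be a study completer with no event coded drug withdrawn. Such a subject might not appear among those who stopped treatment. A subject whose erythema or oozing increases at a target area falls into the same remainder as a subject who did not change. The investigator's own grading of the treated skin would then add nothing to the tolerability assessment.

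**Working it through.** The plan has no figure to reproduce: SAP 4.4 says the 30 subjects have no formal statistical basis. The check is which outcomes the planned tables can display.

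**1. Holds and missed doses**

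| SAP table | What it shows about a hold |
|---|---|
| AE tables (4.3.1) | The triggering event, if reported as an AE, but not that dosing was held |
| AEs leading to discontinuation (4.3.1) | Only if coded drug withdrawn |
| Disposition (4.1.2) | Only if the subject leaves the study |
| Exposure (4.1.7) | Lower weight and volume; effect on duration unknown, as no formula is given |
| Laboratory (4.3.5) | Hepatobiliary and renal counts only; none for the haematology hold thresholds |

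No row gives the number of subjects held, the reason, the length or whether dosing resumed. No row gives missed doses. A laboratory-triggered hold need not have an AE record at all.

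**2. SAD transitions.** Four grades at baseline and four at a visit give 4 × 4 = 16 transitions per sign: 6 improved, 4 unchanged, 6 worsened. The worsened ones are 0→1, 0→2, 0→3, 1→2, 1→3 and 2→3. None has a category. If the SAP's three lines are read separately, 0→1 is counted favourably (score of 1 or less). The other five fall outside every line, together with the unchanged 2→2 and 3→3.

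**3. PGA transitions.** From an entry score of 3 or 4, the outcomes outside PGA of 1 or less are 3→2, 3→3, 3→4, 4→2, 4→3 and 4→4. The worsening 3→4 is pooled with three improvements and two unchanged results.

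**4. Two datasets that the tables cannot tell apart (assumed).** Take 30 subjects, all at grade 2 for one SAD sign, of whom 15 go to grade 1.

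- Dataset A: the other 15 stay at 2, so 0 worsen.
- Dataset B: 5 stay at 2 and 10 go to 3, so 10/30 = 33.3% worsen.

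Both give score 0 in 0/30, score of 1 or less in 15/30, and improved in 15/30 = 50%. For PGA, start all 30 at 3, move 15 to 1, and move 0 or 10 of the rest to 4. Both SAP lines again agree: 15/30 and 0/30.

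**5. Scale at N = 30.** The documents give no expected rates, so these counts are assumed. The intervals are exact (Clopper–Pearson) 95% limits, given only for scale, since the plan is descriptive.

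| Subjects with a hold, or worsened | Percent | 95% limits |
|---|---|---|
| 0/30 | 0% | 0 to 11.6% |
| 1/30 | 3.3% | 0.1 to 17.2% |
| 3/30 | 10% | 2.1 to 26.5% |
| 6/30 | 20% | 7.7 to 38.6% |

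The chance that at least one subject is affected, 1 − (1 − p)^30, is 45% at p = 2%, 79% at 5% and 96% at 10%. Planned exposure is 28 days × 2 = 56 applications. An assumed 7-day hold loses 14/56 = 25%, and a 14-day hold loses 28/56 = 50%.

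**The case against.** The SAP is less blind than a quick reading suggests. Four stronger readings are tempting, and the documents do not support them.

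- **Only events coded drug withdrawn are counted.** That code defines one of five tabulations. A severe related event that triggers a hold still enters the all-event, related and maximum-severity tables.
- **Worsening appears in no table.** Protocol 13.2.1.1 counts as an adverse event "the deterioration of a pre-existing medical condition following or during exposure to a pharmaceutical product", so a reported flare or irritation is tabulated. Protocol 13.3.4 opens with a non-directive question, but it allows directed follow-up and requires any event noted to be reported. SPA and BSA are assessed on target areas, and EASI by body region. The SAP gives the maximum change for all three, and a positive maximum reveals worsening.
- **A late hold can never become a withdrawal.** One AST/ALT criterion in Protocol 9.3 involves elevation "persisting for 2-weeks of study medication interruption or second event of" a further elevation. The second event is itself a separate route, as is the combination with bilirubin or symptoms. The criteria concern discontinuation from the study, which runs to Visit 6, so the end of dosing is not a cut-off.
- **The tolerability result is biased.** That depends on how sites code a hold that is never resumed. Neither the CRF nor its coding options are in the documents.

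It can also be said that SAD is a secondary efficacy measure, that worsening mixes flare with irritation, and that event and exposure listings can be read by eye at N = 30.

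All of this narrows the point without removing it. A maximum shows one extreme value, not how many subjects worsened. None of SPA, BSA or EASI tabulates erythema, induration or oozing by target area. Listings do not replace a summary of the primary outcome.

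**Conclusion.** The point holds as a gap in reporting. The SAP specifies no table of treatment interruptions or missed doses, and its only action-taken table is for drug withdrawn, so a hold never resumed may not be counted as stopping treatment. SAD and PGA are tabulated for favourable outcomes only, so no table counts subjects who worsened at the target areas. Adverse events and the SPA, BSA and EASI maxima give a partial view.

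Each affected subject is 3.3% of 30. How many there would be cannot be estimated from the documents. The conclusion is that the planned tables cannot show these outcomes as counts, not that the result would be wrong or lean one way.

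It rests on two assumptions: that the separate data-handling document mentioned in SAP 4.3 adds no such tables (it is described as covering data handling and programming), and that the CRF records holds. The change is worth making before analysis because tolerability is part of the primary outcome and most of the data should already be collected.

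**What to change.** **SAP 4.3.1 and 4.1.7.**
- Tabulate adverse events with action taken recorded as drug interrupted.
- Give the number and percentage of subjects with any hold, whether triggered by an adverse event or a laboratory value, by reason, duration and whether dosing resumed. The count must be per subject, because a laboratory hold may have no AE record.
- Show holds never resumed alongside discontinuations.
- Summarise missed applications, and state whether hold days are subtracted from duration of treatment.

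**SAP 4.2.2 and 4.2.3.**
- In place of one-sided summaries, give improved, unchanged and worsened counts by visit for each SAD sign and for PGA. Keep the PGA responder proportions planned in Protocol 14.2.
- Limit these to the target areas identified at baseline, because Protocol 12.4 excludes new areas from SAD.
- State how grades from several areas become one result per subject. An any-area rule makes worsening more likely in subjects with more areas.
- Cross-reference the worsening counts from the tolerability results.

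**SAP 4.5.** Protocol 14.1 planned mean changes for ordinal scores, including PGA and SAD. The SAP drops them for these two without saying so. Restore them or record the removal.

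**Cost.** A few extra tables and no new assessment, provided the CRF records holds. Without a control arm, SAD and PGA worsening cannot separate disease flare from local irritation, and each table should say so.

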#### **4.3.2 Physical Examinations**

Physical examination findings will be listed for each subject.

#### **4.3.3 Vital Signs**

Systolic blood pressure, diastolic blood pressure, heart rate, respiratory rate and temperature will be summarized using descriptive statistics for each visit. Both actual values and changes from baseline will be summarized.

#### **4.3.4 ECG assessments**

The core laboratory's interpretation of the ECGs will be summarized as "shift" from baseline to "worst" overall interpretation recorded after baseline where the order of severity of the interpretations from best to worst will be "Normal", "Abnormal, NCS" and "Abnormal, CS".

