9. History of, current or suspected systemic or cutaneous malignancy and /or lymphoproliferative disease, other than subjects with: a history of adequately treated and well healed and completely cleared non-melanoma skin cancers (basal or squamous cell carcinoma) treated successfully at least 1 year prior to study entry with no evidence of disease.

10. Evidence of active or latent bacterial (including tuberculosis) or viral infections at the time of enrollment or history of incompletely treated or untreated tuberculosis. Subjects who have completed therapy for latent tuberculosis may participate.
11. History of a serious local infection (*e.g.*, cellulitis, abscess) or systemic infection including but not limited to a history of treated infection (*e.g.*, pneumonia, septicemia) within 3 months prior to Visit 2. Subjects on an antibiotic for a non-serious, acute local infection must complete the course prior to enrollment into the study.
12. Positive serological test for HIV(antibody), HCV (antibody), or HepB (HBsAg).
13. Subjects with herpes zoster or cytomegalovirus (CMV) that resolved less than 2 months before study enrollment. Subjects with a history of frequent outbreaks of Herpes Simplex Virus (defined as 4 or more outbreaks a year).
14. Screening ECG findings of:
 - a. QTcF >450msec for males or >470msec for females (use of the ECG algorithm is acceptable for this purpose)
 - b. Resting heart rate \leq 45 or Heart Rate \geq 100 beats/minutes if considered to be caused by a clinically significant pathology. The investigator may enter a patient with a HR outside of these values if considered to have no clinical significance.
 - c. Rhythm disturbance other than sinus arrhythmia or ectopic supraventricular rhythm (ectopic atrial rhythm)
 - d. Conduction disturbance including PR >240msec, pre-excitation (delta wave and PR <120msec), second degree or higher AV block
 - e. Acute or chronic signs of ischemia
 - f. Left Bundle Branch Block
 - g. Prior myocardial infarction
15. Subject has participated in an investigational drug trial within 30 days prior to Visit 1.

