- Any subject who develops any of the following ECG findings during the active treatment phase will be instructed to stop study medication and will be withdrawn from the study:
 - Clinically significant rhythm disturbance other than sinus rhythm or ectopic supraventricular rhythm (ectopic atrial rhythm)
 - Clinically significant conduction disturbance including PR $> 240 \text{ msec}$, pre-excitation (delta wave and PR $< 120 \text{ msec}$), second degree or higher AV block
 - New finding of QRS $> 120 \text{ ms}$ (if not present at screen. For example, subjects with Right Bundle Branch Block at screening would not need to be withdrawn from the study if their subsequent ECGs remained unchanged).
 - Evidence of QT-interval prolongation, defined as an increase in the QTcF interval $> 60 \text{ ms}$ from Visit 1
 - Acute signs of ischemia or infarction
 - Any ECG abnormality which may, in the opinion of the investigator, represent a new medical issue of concern

A subject that experiences any of the above events must be discontinued from study medication treatment, the site staff must inform the Aclaris medical monitor of the event, and the site staff must perform protocol-required procedures for trial discontinuation and follow-up.

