13.1.4. Electrocardiogram (ECG)

Standard 12-lead ECGs will be performed by a qualified staff member at Screening (Visit 1), Day 8 (Visit 3), Day 15 (Visit 4), Day 29 (Visit 5) and Day 56 (Visit 6/End of Study). The ECGs must be obtained using a standard 12-lead ECG with a 10mm/mV amplitude, at 25mm/sec and a 5 to 10 second duration. To ensure a steady heart rate the subject must rest quietly in the supine position for at least 5 minutes prior to performing the ECG.

A central cardiology laboratory will provide ECG equipment, supplies and site training. In addition, the central cardiology laboratory will process ECGs received by the sites and report results via a secure study portal. The ECG results will be interpreted by a qualified health professional (evaluator) and the interpretation reported either directly on the tracing or in a separate report. The evaluator will interpret the results of every ECG and define the ECG as “normal” or “abnormal”. Variations such as minor ST changes (i.e., <0.5mm depression) and early re-polarization are considered normal.

The investigator must review the evaluator’s interpretation of each subject’s screening ECG prior to Visit 2. The investigator will review the evaluator’s interpretation of all ECG reports in a timely manner and comment on the clinical relevance of any result that is defined by the evaluator as abnormal.

Any abnormalities that are, in the opinion of the investigator, clinically significant, must be reported as history if found prior to the start of the first dose of study medication or as an AE if found after the start of the first dose of study medication

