14. STATISTICS

14.1. Statistical Methods

Safety and efficacy results will be summarized and presented by visit, with no inferential statistics presented. Parameters related to safety and tolerability will be treated as primary analysis variables. Efficacy parameters will be treated as secondary endpoints.

All data will be summarized by visit, with presentations based on the nature of the parameter. For binary data such as presence or absence of treatment-emergent adverse events, the incidence will be presented along with the overall number of subjects and percentages. External clinical laboratory and similar externally sourced data will be summarized as binary outcomes based on the determination of values beyond applicable normal ranges, and in some cases the assessment of clinical significance of deviations from normal ranges. For ordinal categorical data including efficacy data from PGA, EASI, SPA and SAD scores, and continuous data such as affected body surface area, summary statistics will be presented including N, mean, median, standard deviation, and standard error, by visit. Where applicable, the mean changes from baseline for ordinal categorical and continuous parameters will be presented by visit, along with N, median, standard deviation and standard error.

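### SAP 4.3.4 credits the core laboratory with a clinical-significance grade that the protocol assigns to the investigator, and no ECG interval is summarised although withdrawal rules depend on QTcF change and QRS

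*SAP*

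**What the plan says.** **SAP 4.3.4 (ECG assessments).** The whole ECG analysis is one sentence: "The core laboratory's interpretation of the ECGs will be summarized as" a shift from baseline to the worst "overall interpretation recorded after baseline where the order of severity of the interpretations from best to worst will be" Normal, then Abnormal NCS, then Abnormal CS. No other SAP section mentions QT, QTcF, PR or QRS.

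**Protocol 13.1.4 (Electrocardiogram).** After collection, "the central cardiology laboratory will process ECGs received by the sites and report results via a secure study portal". On reading: "The evaluator will interpret the results of every ECG and define the ECG as" normal or abnormal. The investigator then has to "comment on the clinical relevance of any result that is defined by the evaluator as abnormal".

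**Protocol 9.3 (Subject Withdrawal Criteria).** One ground for withdrawal during active treatment is "Evidence of QT-interval prolongation, defined as an increase in the QTcF interval" of more than 60 ms from Visit 1. Another is a QRS above 120 ms that was not there at screening. PR above 240 ms also appears, as an example of a conduction disturbance that is clinically significant.

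**Protocol 9.2 (Subject Exclusion Criteria).** Entry is barred for "QTcF >450msec for males or >470msec for females".

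**Protocol 14.1 (Statistical Methods).** The general rule is "All data will be summarized by visit, with presentations based on the nature of the parameter".

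**SAP 4.3.3 and 4.3.5.** Vital signs and laboratory parameters get actual values and changes from baseline at each visit. Laboratory data also get counts of subjects meeting hepatobiliary and renal criteria.

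**The concern.** There are two separate problems.

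The first is the source of the variable. The SAP takes a three-level grade from the core laboratory, but the protocol describes a two-level reading by the evaluator and a later comment on relevance by the investigator. A programmer cannot build the planned table from those descriptions without choosing a source that the SAP does not name. If the NCS and CS rows are filled from site comments, the reader is told that a central laboratory made a judgement that the site made.

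The second is the missing content. Safety and tolerability are the primary outcome, the analysis is purely descriptive, and SAP section 2 lists ECGs among the five assessments that inform it. Two of the protocol's ECG withdrawal rules are numerical statements about intervals, yet no planned summary shows an interval, a change in one, or how many subjects crossed a threshold. Someone who reads only the ECG table could conclude that tracings were unremarkable when a subject had a QTcF rise large enough to require withdrawal.

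**Working it through.** The plan states no figure to reproduce on this point. The check compares texts and then applies arithmetic to the protocol's own QTcF limits.

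**Step 1: who produces which grade**

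| Grade | SAP 4.3.4 | Protocol 13.1.4 |
|---|---|---|
| Normal or abnormal | Core laboratory | Evaluator |
| NCS or CS, within abnormal | Core laboratory | Investigator, commenting on relevance |

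The first row can be reconciled if the evaluator works for, or reports through, the core laboratory. The protocol introduces the evaluator directly after the laboratory but does not state this. The second row cannot be reconciled from the text, because the protocol describes no central three-level reading.

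**Step 2: what is summarised**

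ECGs are scheduled at Visits 1, 3, 4, 5 and 6. SAP 4.3 takes as baseline the last value available up to the date of first application. No ECG is scheduled at Visit 2, so the scheduled baseline is Visit 1, the same reference that the QTcF withdrawal rule uses. Change from baseline is therefore directly comparable with the 60 ms rule, but the SAP does not tabulate it.

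**Step 3: can a subject who meets the QTcF rule be shown as Normal to Normal?**

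Inputs:
- Withdrawal rule (Protocol 9.3): rise *d* > 60 ms from Visit 1, with no absolute QTcF limit.
- Upper edge of a normal reading, *L*: the documents do not give one. Assumption: *L* equals the entry limit in Protocol 9.2, 450 ms for men and 470 ms for women.

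For Visit 1 value *b*, the later tracing stays within *L* when *b* + *d* ≤ *L*. With *d* > 60 this is possible only if *b* < *L* − 60.

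| | *L* | *b* must be below *L* − 60 | Example inside | Example outside |
|---|---|---|---|---|
| Men | 450 ms | 450 − 60 = 390 ms | 380 + 61 = 441, under 450 | 400 + 61 = 461, over 450 |
| Women | 470 ms | 470 − 60 = 410 ms | 400 + 61 = 461, under 470 | 420 + 61 = 481, over 470 |

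At the edge, 389 + 61 = 450 and 409 + 61 = 470, both still within the limit.

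**Step 4: sensitivity to the assumption**

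The boundary moves one for one with *L*. If evaluators treated 430 ms as the top of normal, the boundary would be 430 − 60 = 370 ms; at 440 ms it would be 380 ms. A lower *L* narrows the range of Visit 1 values but does not remove it. It would be removed if evaluators called any rise above 60 ms abnormal whatever the absolute value. The documents give no rule either way.

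The documents give no QTcF distribution, so the number of subjects likely to be affected cannot be estimated.

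**The case against.** **The withdrawal is not lost.** SAP 4.1.2 tabulates reasons for discontinuation. Protocol 13.1.4 requires ECG abnormalities that the investigator judges clinically significant after first dosing to be reported as adverse events, and SAP 4.3.1 tabulates events that led to drug withdrawal. This stands. A reader might infer that QTcF withdrawals would vanish from the report, and the documents do not support that. Those tables show that a subject stopped. They do not show the size or timing of the interval change, or any smaller drift across subjects.

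**Protocol 14.1 allows something close to SAP 4.3.4.** The same paragraph as the by-visit rule lets externally sourced data be summarised as binary outcomes against normal ranges, in some cases with clinical significance. Central ECG results plausibly fall under this. It is therefore not shown that leaving out interval means is a departure that SAP 4.5 had to declare. What remains is that one worst-value shift is not a by-visit summary.

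**The abnormal rows may not be empty.** A reader might infer that a two-level central reading leaves the CS row empty by construction. The text does not prove this: the evaluator is not said to be laboratory staff, and the laboratory's report format is not in the documents.

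**Other ECG rules do reach the table.** The PR rule already requires clinical significance, and the rhythm and ischaemia rules are matters of interpretation, so an interpretation shift can reflect them. Nothing shows that a new QRS above 120 ms would be read as normal. The Normal-to-Normal demonstration is for QTcF only.

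**Smaller points that stand.** Heart rate is already summarised by visit in SAP 4.3.3. A worst post-baseline shift is a reasonable safety display. In a single-arm open-label study, the investigator's knowledge of treatment biases no comparison, so the issue is labelling.

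**The separate data-handling document** mentioned in SAP 4.3 was not available. The SAP describes it as covering data handling and programming specifications, so it might name data sources but would not be expected to add analyses.

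**Conclusion.** The point holds in two parts. First, SAP 4.3.4 attributes the NCS/CS grade to the core laboratory, while the protocol gives that judgement to the investigator. As written, an investigator's judgement would be presented as a central reading. Second, the worst-interpretation shift is the only planned ECG summary, and it contains no interval, although the protocol withdraws subjects on QTcF change and on new QRS widening.

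On size: if normal extends to 450 ms (men) and 470 ms (women), a subject with a Visit 1 QTcF below 390 ms or 410 ms respectively can meet the QTcF rule and still appear as Normal to Normal. This *can* happen. Nothing shows that it will, or how often, because it depends on how evaluators treat a large rise within the limit.

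The documents do not support concluding that ECG withdrawals would go unreported, that the CS row must be empty, or that every interval-based rule is hidden. This is a cheap improvement to the primary safety summary; it does not invalidate the analysis.

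**What to change.** In SAP 4.3.4:

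1. Tabulate the evaluator's reading as a two-level Normal/Abnormal shift. Tabulate the NCS/CS assessment of abnormal tracings separately, labelled as the investigator's.
2. Add values and changes from Visit 1, by visit, for QTcF, PR and QRS. Heart rate need not be repeated.
3. Count subjects who meet the existing Protocol 9.3 thresholds: QTcF rise above 60 ms from Visit 1, and QRS above 120 ms when not present at screening. Show PR above 240 ms alongside the investigator's clinical-significance call, because the protocol's rule depends on that call. The rules apply to the active treatment phase, so show Visits 3 to 5 separately from the Visit 6 follow-up.
4. Record the change in SAP 4.5.

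The cost is a wording change and one or two extra descriptive tables. The withdrawal rules already require these intervals to be measured, so no visit, procedure or clinical rule changes.
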